## 6.5. Sample Size Determination

To estimate the number of sample size, two things are taken into account: The number of subjects from previous studies, and the minimum number [8] to show whether the primary objective is met. We plan to include 40 patients for the study.

- Research hypotheses: The completion rate is greater than or equal to 95% (point estimate).

The completion is defined that surgery completion without conversion (to laparoscopic or open surgery) due to system serious malfunction, and without any major complications within 24-hour post-surgery. Therefore, when a subject who inevitably converted not due to the Hugo™ RAS system, it is not considered as a surgery failure as per the definition and the subject will be excluded from the primary endpoint analysis. Also, a complication within 24-hour post-surgery will not be considered as a surgery failure unless it falls under the definition of major complication.

According to previous literature on adverse events in robotic surgeries over 14 years using da Vinci, the average rates of device malfunctions and failure-related conversions was 3% (varied between 0.4% and 8.0%) and 0.9% (varied between 0.1% and 2.7%), respectively [9]. In Korea, the reported rate of system malfunctions and failures was less than 2% among over 10,000 da Vinci robotic procedure cases between 2005 to 2013. However, no cases of malfunction led to conversion to open or laparoscopic surgery [10].

---

 According to the Korean Clinical Practice Guideline for the Treatment of Prostate Cancer (The Korean Urological Oncology Society, 2020)[7], radical prostatectomy is an appropriate therapy for any patient with clinically localized prostate cancer that can be completely excised surgically, who has a life expectancy of  $\geq 10$  years, and who has no serious comorbid conditions that would contraindicate an elective operation.

 Relative contraindications for laparoscopic cholecystectomy include followings: Inability to tolerate general anesthesia due to cardiopulmonary diseases, hemodynamic instability, pregnancy (3rd trimester), malignant tumors, liver cirrhosis and portal hypertension, and intestinal adhesions (Kim & Seo. Hepato-Biliary-Pancreatic Surgery (4th ed.). 2019)

  $N \geq 30$  according to the central limit theorems

With regards to the previous studies, the completion rate of surgery—the primary endpoint of this study—is expected to be over 90%. The study will be considered successful when the point estimate of the completion rate is greater than or equal to 95%, which is when  $\leq 2$  patients (among 40) does not reach the surgery completion. The primary endpoint is evaluated within short period (i.e., 24-hour post surgery) period so the dropout rate is not considered. Note that it is not possible to assess the surgery completion per the study definition when a subject who inevitably converted not due to the Hugo™ RAS system. In such cases, new enrollment is allowed until the minimum sample size (i.e., 40) is reached.

In summary, the estimated sample size is adequate to demonstrate the safety and performance of the investigational device regarding following reasons: (1) the estimated sample size is higher than the number of patients from recent pivotal trial (which used the same primary endpoint) of the locally commercialized product (i.e., 32; 17 prostatectomy cases and 15 cholecystectomy cases) [11, 12], and (2) the investigational device is intended to be used for the same patient population of the commercialized product.

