## 6. Selection of Subjects

### 6.1. Study Population

A minimum of 40 subjects will be enrolled at single site in Korea. The subjects must be acceptable candidates for a fully robotic assisted procedure with the Medtronic Hugo™ RAS System, as determined by the principal investigator.

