### 6.2. Subject Enrollment

A subject is considered enrolled in the study when the consent process is signed and dated. Subject enrollment will be consecutive at the institution according to required procedure types and eligibility criteria.

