### 7.2. Design

This study is a prospective, single-center, single-arm, pivotal trial in 40 patients undergoing prostatectomy (20) or cholecystectomy (20) using the Medtronic Hugo™ RAS System. Subjects will be followed for 30 days post procedure. As this study is a single-arm trial, no randomization or blinding will be applied.

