***Medtronic Business Restricted***

The IC process must be conducted by the principal investigator or an authorized designee. The process of IC must be conducted without using coercion or undue improper influence on or inducement of the subject to participate by the investigator or other study site personnel. The IC process shall not waive or appear to waive subject's legal right. The language used shall be as non-technical as possible and must be understandable to the subject.

Subjects will be informed that despite signing IC, the screening assessment may demonstrate the subject is not a suitable candidate for the study or the procedure and may be withdrawn. Subjects will also be informed that after the investigation visits are completed, the subjects will receive the standard medical care, just as they would have had they not participated in the study.

Prior to enrolling subjects, the site IC must be approved by the IRB. The document(s) must be controlled (i.e., versioned and/or dated) to ensure it is clear which version(s) were approved by the IRB. Any adaptation of the sample IC must be reviewed and approved by Medtronic and the IRB reviewing the application prior to enrolling subjects.

A copy of the IC signed and dated as required by law, must be provided to the subject. The original of the signed ICF (and any other privacy language if required) must be filed with the subject's study documents and made available for review by sponsor site monitors, auditors, or regulatory inspectors.

It is best practice for the IC process to be documented in the subject's case history, regardless of circumstance. If the IC is obtained the same day the subject begins participating in study-related procedures, it must be documented in the subject's case history that consent was obtained prior to participation in any study-related procedures.

The investigator must notify the subject of any significant new findings about the study that become available during the course of the study which are pertinent to the safety and well-being of the subject, as this could impact a subject's willingness to participate in the study. If relevant, consent may be requested from subjects to confirm their continued participation.

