***Medtronic Business Restricted***

## 9. Statistical Design and Methods

### 9.1. General Aspects of Analysis

The study analysis will occur after all patients complete the 30-day follow-up and data entry error or non-reasonable values are cleaned. Data analysis will be performed by Medtronic or its designee using SAS for Windows (version 9.4 or higher, SAS Institute Inc. Cary, NC) or other widely accepted statistical or graphical software.

Statistical tests will be conducted at a two-sided alpha level of 0.05. Confidence intervals will be presented as 95% confidence intervals.

The following populations will be considered for the analysis of data for this study:

- Full Analysis Set (FAS): The full analysis set is defined as all enrolled subjects in whom the Hugo™ RAS procedure is begun (defined as the first skin incision). In the event that a subject is consented but the first incision does not occur (e.g., if the subject becomes ineligible during the timeframe between consent and the procedure day), that subject will be excluded. Also, a subject who inevitably converted (to open or conventional laparoscopic surgery) not due to the Hugo™ RAS system will be included in the safety and other descriptive analyses but excluded from the primary endpoint analysis (since the subject is not evaluable).
- Per Protocol Set (PPS): The per protocol set is a subset of the FAS including only those without any major protocol deviations. Following subjects from the FAS will be excluded from the PPS:
  - Subject who inevitably converted (to open or conventional laparoscopic surgery) not due to the Hugo™ RAS system
  - Subject did not meet Inclusion/exclusion criteria
  - Subject chooses to withdraw
  - Failure to collect required study data up to 30-day post-surgery

The FAS will be the primary analysis set for the evaluation of the primary and secondary endpoints. Statistical analysis will be performed for each analysis set. However, if all subjects complete the study per the CIP, the results can be presented regardless of the analysis set.

Subject disposition will be illustrated in a CONSORT diagram. All enrolled subjects will be included in a subject disposition table indicating reasons for exclusion from the FAS and PPS analysis sets.

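### Does the success rule of at most 2 failures among 40 break down because the plan never fixes the analysed number at 40?

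*Protocol*

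**What the plan says.** Protocol section 6.5 declares success when the point estimate of the completion rate reaches 95%, and translates this as no more than 2 "patients (among 40) does not reach the surgery completion". Sections 9.1 and 9.4 and SAP section 7.9 carry only the proportion of 0.95. Section 9.1 applies it in the Full Analysis Set (FAS).

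The number 40 appears with different meanings:

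- Section 6.1: "A minimum of 40 subjects will be enrolled at single site in Korea". Section 6.2 then defines enrolment: "A subject is considered enrolled in the study when the consent process is signed and dated". Read literally, this is 40 consents.
- Section 7.2 and SAP section 5 describe 40 patients undergoing surgery, 20 per procedure. This is 40 operated subjects.
- Section 6.5 permits replacement of subjects whose completion cannot be assessed: "In such cases, new enrollment is allowed until the minimum sample size (i.e., 40) is reached". This implies 40 assessable subjects.

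Two kinds of subject can leave the primary analysis. Section 9.1 takes out of the FAS those who never reach surgery ("In the event that a subject is consented but the first incision does not occur"). Subjects converted for reasons other than the system stay in the FAS but are left out of the primary endpoint, and the replacement clause in 6.5 covers only these. Section 6.5 also makes no allowance for loss, because the endpoint is read within 24 hours of surgery ("so the dropout rate is not considered"). Neither the synopsis nor section 6.1 states a maximum.

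**The concern.** The planned number sits exactly on a step of the rule. One fewer analysed subject lowers the permitted failures from 2 to 1, and the plan does not say in one place that 40 evaluable subjects are required. The reason given for ignoring dropout covers loss after surgery. It does not cover loss between consent and incision, which section 8.2 foresees: "the screening assessment may demonstrate the subject is not a suitable candidate for the study or the procedure and may be withdrawn".

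Three consequences seem to follow:

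1. Two failures would miss the endpoint with 39 analysed and meet it with 40, so a screening exit could decide a pivotal trial.
2. The trial is open and single-arm, so failures are known as they occur. A site with 2 failures in 39 could choose to add one more subject, and a completed case would turn a miss into a success.
3. With no stated maximum, 3 failures in 40 (92.5%) could be extended to 57/60 (95.0%).

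If these held, the primary conclusion would depend on enrolment choices made with the results in view.

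**Working it through.** **Inputs.** Threshold 0.95 and planned number 40 (protocol 6.5). The protocol expects a completion rate above 90% but names no value, so true rates of 90%, 95% and 98% are assumed; f is the true failure rate (0.10, 0.05, 0.02). X is the number of failures, taken as binomial.

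**Step 1: the plan's own figure.** The largest k with (n − k)/n ≥ 0.95 is floor(0.05n). At n = 40 this is 2, and 38/40 = 95.00%. The figure in 6.5 is reproduced.

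**Step 2: the step.** One failure passes for n = 20 to 39, two for 40 to 59, three for 60 to 79. At n = 39, 37/39 = 94.87% misses and 38/39 = 97.44% passes.

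**Step 3: chance of success, P(X ≤ k).**

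| Analysed (k) | true 90% | true 95% | true 98% |
|---|---|---|---|
| 39 (1) | 8.8% | 41.3% | 81.7% |
| 40 (2) | 22.3% | 67.7% | 95.4% |
| 45 (2) | 15.9% | 60.8% | 93.9% |

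**Step 4: does an optional 40th subject inflate success?** With 0 or 1 failures in 39, the trial passes with or without one more subject. With 3 or more, it fails either way. Only exactly 2 failures matter, and then the 40th subject must complete:

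P(success) = P(X ≤ 1 | 39) + P(X = 2 | 39) × (1 − f)

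- true 90%: 0.0876 + 0.1502 × 0.90 = 0.2228
- true 95%: 0.41295 + 0.27767 × 0.95 = 0.6767
- true 98%: 0.81678 + 0.14036 × 0.98 = 0.9543

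These are the fixed-40 values in Step 3. Choosing to top up after seeing the results reproduces the planned design and gains nothing beyond it.

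**Step 5: the shortfall scenario.** Suppose exactly 40 consents, no replacement, and a consent-to-incision loss of 2.5%, 5% or 10%. These loss rates are assumptions; the documents give none. The chance of fewer than 40 in the FAS is 1 − (1 − loss)^40 = 63.7%, 87.1%, 98.5%. Averaged over the resulting FAS size, success at a true 95% is 51.4%, 46.3%, 46.1% instead of 67.7%. At a true 98% it is 86.9%, 84.3%, 84.0% instead of 95.4%.

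**Step 6: running on to 60 after exactly 3 failures in 40.** All 20 extra subjects must complete:

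P(success) = P(X ≤ 2 | 40) + P(X = 3 | 40) × (1 − f)^20

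At a true 95% this is 0.6767 + 0.1851 × 0.3585 = 0.7431. At a true 90% and 98% it is 24.7% and 97.9%.

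**Step 7: would permitting a range from 40 to 59 help?** The permitted count stays at 2 throughout, but at a true 95% the chance of success falls from 67.7% at n = 40 to 42.9% at n = 59, close to the 41.3% at n = 39. Such a range keeps the count of 2 valid and leaves the operating characteristics as variable as before.

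**The case for a change.** The strongest case for acting is that a pivotal trial should state which 40 it means. Read literally, sections 6.1 and 6.2 are satisfied by 40 consents, and 38 or 39 analysed would then comply with the text. Replacement is permissive, is tied to one cause, and is absent from SAP section 6. Losing one subject costs 26.4 percentage points of success probability at a true 95% (67.7% − 41.3%), and that cost falls on the sponsor. One clarifying sentence would be cheap.

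The inconsistency in wording stands, and so does the arithmetic. The consequences do not:

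- The shortfall needs a site that treats a minimum as a stopping point. No section says to stop at 40 consents, while the design section and SAP section 5 describe 40 operated patients and 6.5 allows enrolment until 40 is reached.
- The baseline visit may take place on the day of surgery (section 8.4), so the 28-day window is an outer limit and not evidence of loss.
- Running on to 60 needs 20 more operated patients, half the planned trial again, against a plan of 40, consecutive enrolment (section 6.2) and three months for enrolment and follow-up together (section 7.1). The missing maximum is real, but this use of it is remote. Even then the gain at a true 95% is from 67.7% to 74.3%.

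**Conclusion.** The concern does not call for a change. Section 6.5 is correct at 40, and the decision rule, a proportion of at least 0.95, is defined at whatever number is analysed. A step in the permitted count is unavoidable with a discrete outcome, and no choice of number removes it. The data-dependence argument fails exactly: an optional top-up from 39 to 40 gives 22.3%, 67.7% and 95.4% at assumed true rates of 90%, 95% and 98%, the same as fixing 40 in advance.

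What is left is a gap in wording: whether 40 means consented, operated or assessable, and whether subjects who never reach incision are replaced. Sections 6.5 and 7.2 together point to 40 operated and assessable subjects, and the sponsor has every reason to enrol to that number, since a shortfall mainly lowers its own chance of success. If fewer were analysed, the 0.95 rule would still give a clear answer, and a stricter one just below 40. A table of permitted failures or added success probabilities would change no result.

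This rests on binomial outcomes, on the assumed true rates, and on a site that does not close at 40 consents. If the site did close there, the figures in Step 5 would apply, subject to their assumed loss rates.

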## 7. Study Method

### 7.1. Duration

The expected study duration is approximately 9 months after protocol approval

- IRB submission and site activation: 3 months
- Subject enrollment to follow-up completion: 3 months
- Statistical analysis and report writing: 3 months

### 7.2. Design

This study is a prospective, single-center, single-arm, pivotal trial in 40 patients undergoing prostatectomy (20) or cholecystectomy (20) using the Medtronic Hugo™ RAS System. Subjects will be followed for 30 days post procedure. As this study is a single-arm trial, no randomization or blinding will be applied.

### 7.3. Rationale

This trial will collect patient data undergoing two representative procedures (i.e., prostatectomy, cholecystectomy) in robotic surgery field to minimize potential confounding effect due to surgeon's proficiency or learning curve.

The study is designed as single-arm trial due to following logistics issues: Room to setup the investigational device, space for storage, and the number of commercialized products at the study site.

The primary endpoint of this study is the completion rate, which is defined as a proportion of subjects who completed the surgery without conversion due to system serious malfunction, and without any major complications within 24-hour post-surgery. Recent pivotal trial approved from the MFDS also utilized completion rate as the primary endpoint [11, 12].

## 8. Study Procedures

### 8.1. Schedule of Events

Data collection requirements are summarized in Table 5.

**Table 5. Data Collection and Study Procedure Requirements at Subject Visits**

Procedure/Assessments	Baseline	Surgery	Discharge	Follow-up 		
	-28D~0D	0D	0D~Day of discharge	7D (±3D) 	14D (±3D) 	30D (±7D)
Informed consent	X					
Eligibility check	X					
Demographics	X					
Medical history	X					
Laboratory tests 	X		X 		X	X
Vital signs	X	X	X 		X	X
Indication under study 	X					
Procedure information 		X				
Device deficiency		As they occur				
Pathological exam 			X			
Post-operative imagings 			X	X		
Medication 	X	X	X	X	X	X
Adverse event 	As they occur					
Protocol deviation	As they occur					
Readmission/Reoperation				As they occur		
Study Exit						X

1) If any unscheduled visit occurs other than planned follow-up visit, subject's data (e.g., adverse event, medication, etc.) can be collected if applicable.

2) Applicable for prostatectomy subjects only.

3) Laboratory tests include complete blood cell and serum chemistry.

4) Timing of laboratory tests and vital sign assessments up to discharge will be immediately after surgery (Day 0; laboratory tests only), Day 1, and Day 3 for prostatectomy subjects, and Day 1 for cholecystectomy subjects.

5) Procedure-specific information will be collected each for prostatectomy or cholecystectomy.

6) Applicable for prostatectomy subjects only.

7) Applicable for prostatectomy subjects only. Post-operative imaging includes chest X-ray (AP view), abdomen X-ray (Supine or erect view), KUB X-ray, and cystography. The cystography will be conducted on Day 7, while other radiographs will be obtained on immediately after surgery (Day 0; except KUB X-ray), Day 1, and Day 3. Post-operative imaging findings will be only collected to in the CRF if it is related to adverse events.

8) Following study-related medications will be collected: Pre-procedure anticoagulants or monoamine oxidase inhibitors (which may affect hemostasis) within 30 days prior to surgery, any relevant medication related to the

**Medtronic Business Restricted**

**CONFIDENTIAL**

056-F275 Rev E Clinical Investigation Plan Template

study indication, pain medications due to an adverse event, medications given as treatment for an adverse event. Medication will be coded using WHO Drug Dictionary.

9) Adverse events will be collected after subject has agreed to participate and provided the written informed consent.

The study visits include baseline visit, admission (surgery to discharge), and follow-up visit after discharge:

- Baseline: To determine study eligibility and collect baseline information (demographics, medications, medical history, surgical history, etc.)
- Surgical procedure: To re-confirm eligibility criteria, procedure set-up and take-down, medication changes, intraoperative complication evaluation, disease state evaluation, procedure success, conversion rates, protocol deviation, adverse event evaluation, and device deficiency collection
- Up to hospital discharge: Adverse event evaluation, complication rate, disease state evaluation, medication changes and protocol deviation
- Follow-up after discharge: Adverse event evaluation, complication rate, disease state evaluation, length of hospital stay, readmission (if applicable), reoperation (if applicable), medication changes, protocol deviation and study exit

## 8.2. Subject Consent

Prior to initiation of any study-specific procedures, informed consent (IC) must be obtained from the subject. The informed consent form (ICF) must be personally signed and dated by the subject themselves and the principal investigator or a delegated investigator (physicians only) at the time of consent. The subject has the right to refuse and the refusal will not affect the routine care of the subject.

A subject may only consent after information has been given and explained to the subject on all aspects of the clinical investigation that are relevant to the subject's decision to participate. The subject must have ample time and opportunity to read and understand the ICF, to inquire about details of the study, and to decide whether or not to participate in the study. All questions about the study should be answered to the satisfaction of the subject. When required per regulation, the subject will be required to sign additional forms such as Personal Information Collection and Use Agreement, etc.

In the event the subject or legally designated representative cannot read and/or write, witnessed (impartial witness) IC will be allowed, provided detailed documentation of the process is recorded in the subject's case history and the witness signs and dates the IC. The IC and any other information must be read aloud to the prospective subject or his/her legally designated representative. Whenever possible, either the subject or his/her legally designated representative shall sign and personally date the informed consent form. The witness signs and personally dates the IC attesting that the information was accurately explained and that informed consent was freely given.

***Medtronic Business Restricted***

The IC process must be conducted by the principal investigator or an authorized designee. The process of IC must be conducted without using coercion or undue improper influence on or inducement of the subject to participate by the investigator or other study site personnel. The IC process shall not waive or appear to waive subject's legal right. The language used shall be as non-technical as possible and must be understandable to the subject.

Subjects will be informed that despite signing IC, the screening assessment may demonstrate the subject is not a suitable candidate for the study or the procedure and may be withdrawn. Subjects will also be informed that after the investigation visits are completed, the subjects will receive the standard medical care, just as they would have had they not participated in the study.

Prior to enrolling subjects, the site IC must be approved by the IRB. The document(s) must be controlled (i.e., versioned and/or dated) to ensure it is clear which version(s) were approved by the IRB. Any adaptation of the sample IC must be reviewed and approved by Medtronic and the IRB reviewing the application prior to enrolling subjects.

A copy of the IC signed and dated as required by law, must be provided to the subject. The original of the signed ICF (and any other privacy language if required) must be filed with the subject's study documents and made available for review by sponsor site monitors, auditors, or regulatory inspectors.

It is best practice for the IC process to be documented in the subject's case history, regardless of circumstance. If the IC is obtained the same day the subject begins participating in study-related procedures, it must be documented in the subject's case history that consent was obtained prior to participation in any study-related procedures.

The investigator must notify the subject of any significant new findings about the study that become available during the course of the study which are pertinent to the safety and well-being of the subject, as this could impact a subject's willingness to participate in the study. If relevant, consent may be requested from subjects to confirm their continued participation.

